8.1 Sequence of Analysis

The following analyses will be performed during this trial:

- Interim futility analysis: will be performed 3 months after start of study treatment of the 20th subject. Only the first 20 subjects at the clinical cut-off date will be included in the primary endpoint and secondary efficacy endpoint analysis; ; and all subjects who received at least one dose of treatment up to the cut-off date will be included for analysis of safety.
- Interim efficacy analysis: will be performed 6 months after start of study treatment of the 56th subject. The analysis will be performed on the ITT population and will include subjects with minimum follow up of 6 weeks, 12 weeks and 24 weeks beyond day 1.
- The primary analysis: will be performed 6 months after the accrual of the last subject. The primary analysis will be performed on the ITT population.
- An exploratory analysis will be conducted 12 months after the accrual of the last subject.

The date and time of the first study treatment will be used to select the first 20 and 56 subjects for the interim futility and interim efficacy analysis, respectively. There will be a partial database lock for both interim analyses and the primary analysis.

8.2 Interim Analysis

The interim futility analysis will include the primary endpoint analysis, secondary efficacy endpoint analysis, summary of baseline characteristics, treatment exposure and the safety analysis as outlined in this SAP. If no unconfirmed response according to RECIST 1.1 is seen in the first interim analysis, the enrollment will be stopped until the SMC makes a recommendation as to whether the trial should continue.

The interim efficacy analysis will comprise a full evaluation of all efficacy and safety endpoints as described in this SAP. If the efficacy goals are met at the interim efficacy analysis, enrollment will continue to the planned full number of subjects in order to collect further data on the primary and secondary endpoints.

8.3 Final Analysis

All planned analyses outlined in this SAP will be performed for the primary analysis. A partial database lock will be performed for the primary analysis and the last planned SMC meeting will

be held thereafter. The full DB lock will take place one year after the last subject receives the last dose of avelumab.

In addition, no database can be locked until this SAP has been approved.

Subject follow-up for progression and survival will continue until 1 year after the last subject receives the last dose of avelumab.

9 Changes to the Planned Analyses in the Clinical Trial Protocol

The statistical methods as described in the protocol of the trial were adopted. Additional statistical analyses and summary performed that are not included in the CTP are summarized in details in Section 5.1 Changes to Previous Version.

10 Analysis Sets

Screening Analysis Set

The screening analysis set includes all subjects who signed the informed consent.

Intent-to-Treat Analysis Set

For the interim futility and the interim efficacy analysis, the intention-to-treat (ITT) analysis set includes the first 20 and 56 subjects who received at least one dose of trial treatment, respectively. For the primary analysis, the ITT analysis set includes all subjects who received at least one dose of trial treatment.

The ITT analysis set will be used for all analyses of efficacy, and health-related quality of life and will be the primary population for decision-making.

Safety Analysis Set

The Safety analysis set includes all subjects who received at least one dose of trial treatment at the clinical cut-off date. The Safety set will be used for all safety analyses.

Per Protocol Analysis Set

The Per-Protocol (PP) analysis set is a subset of the ITT analysis set and includes all ITT subjects who meet all of the following criteria:

- Measurable disease per RECIST 1.1 and IERC assessment
- Distant metastatic disease
- Histologically proven MCC with confirmation of the diagnosis by immuno-histochemistry detection of CK20 (or other appropriate cytokeratin expression such as pancytokeratin,

AE1/AE3, or Cam5.2) according to the assessment documented in the “Disease History” eCRF page

- Have progressed after 1 line of chemotherapy that was administered for the treatment of distant metastatic MCC as defined in Section 5.3.1 Inclusion Criteria in the protocol
- Evaluable patients, defined as having at least one post-baseline tumor assessment with absence of non-assessable status

The PP analysis set will be used for additional sensitivity analyses for the primary and secondary efficacy endpoints. If the PP analysis set includes at least 95% of subjects in the ITT analysis set, additional efficacy analyses on the PP analysis set will be omitted as the differences in the results based upon these two analysis sets are expected to be negligible.

Additional Subgroup Analysis Sets

The below subgroup analyses may be performed on primary and key secondary efficacy endpoints. Since the study is not powered for any subgroup analysis, CCI [REDACTED]

The following subgroups will be defined:

- Age Group 1:
 - Age < 65 years (Reference)
 - Age \geq 65 years
- Age Group 2:
 - Age \leq Median (Reference)
 - Age > Median

CCI [REDACTED]

CCI

- Gender
 - Male (Reference)
 - Female
- Pooled Region:
 - North America
 - Europe (Reference)
 - Rest of the World
- Time from initial diagnosis to study entry:
 - ≤ 1 year (Reference)
 - > 1 year and ≤ 2 years
 - > 2 years
- ECOG PS at baseline
 - ECOG PS 0 (Reference)
 - ECOG PS 1
- Disease Burden
 - Baseline SLD \leq Median (Reference)
 - Baseline SLD $>$ Median
- Site of primary tumor
 - Skin
 - No-skin (Reference)
- Presence of visceral metastases at baseline . Target or non-target lesions that are categorized as “metastatic” per investigator assessment are classified as visceral metastases.
 - Present
 - Absent (Reference)
- Number of prior systemic therapies for metastatic disease
 - 1 Prior Therapy (Reference)
 - ≥ 2 Prior Therapies
- Number of prior systemic therapies for metastatic disease or locally advanced therapies
 - 1 Prior Therapy (Reference)

- ≥ 2 Prior Therapies

11 General Specifications for Statistical Analyses

All efficacy analyses will be performed on the ITT population considering subjects as treated. Selected efficacy analyses will be repeated for the PP population only if the size of this population is less than 95% of the ITT population.

The Safety population will be considered for safety analyses.

Data handling after cut-off date:

Data after cut-off do not undergo the cleaning process and will not be displayed in any listings or used for summary statistics, statistical analyses or imputation. The only exceptions are the date of death and the date last known to be alive from the eCRF form “Subject Status / Survival Follow-up”.

Pooling of centers:

Because of the high number of participating centers and the anticipated small number of subjects receiving trial treatment in each center, data will be pooled across centers. The factor center will not be considered for subgroup analyses.

Definition of baseline:

The last non-missing measurement prior to the first study drug administration will be used as the baseline measurement, if not otherwise specified. Additionally, ECG baseline will be derived from the visit where at least HR, PR, QRS, and QT are not missing. QTcF will be derived based on HR and QT. The average of the replicate measurements (prior infusion and post infusion) should be used in deriving baseline values for each parameter.

Definition of study day/treatment day:

Treatment day is defined relative to the first study drug administration.

Treatment day 1 defines the first study drug administration date, the day before is defined as treatment day -1 (no treatment day 0 is defined).

Definition of on-treatment period:

On-treatment period is defined as the time from the first study drug administration to the last drug administration date + 30 days or earliest date of subsequent anti-cancer drug therapy – 1 day, whichever occurs first, unless otherwise stated. If the earliest date of subsequent anticancer drug therapy was a partial date and only day was missing, it was imputed as the last day of the month. If both day and month were missing, no imputation was performed. The imputed date was used for defining on-treatment period as well as confirming CCI

Unscheduled visits:

Data collected at unscheduled visits will be included and analyzed for both safety and efficacy analyses in the same fashion as the data collected at scheduled visits.

Data collected after re-initiated treatment:

Data collected after re-initiation of treatment will not be included for safety and efficacy analyses except for overall survival and disposition.

Visit Window:

The assignment of visit window is described in Table 1 for the purpose of by-visit analyses of safety data:

- Baseline will be derived as described above.
- Both scheduled and unscheduled assessments are included for visit windowing.
- No visit windowing will be performed at Discontinuation, End-of-Treatment, or Safety Follow-up visits for laboratory, vital sign, ECG data, and 2hr post dose assessment on Week 1 Day 1 for ECG data. Instead, the earliest non-missing observation among the unscheduled or scheduled assessments for each visit (Discontinuation, End-of-Treatment, and Safety Follow-up) will be used for the analysis. For 2hr post dose assessment on Week 1 Day 1 ECG data, the earliest non-missing observation on Week 1 Day 1 will be used for the analysis.
- If there are multiple assessments for any specified visit and some of them are from scheduled visits with non-missing assessment results, the assessment from scheduled visit that is closest to the planned study day will be used for analysis.
- If there are multiple assessments for any specified visit and none of them are from scheduled visits, the assessment with non-missing results and closest to the planned study day will be used for analysis.
- If there are two or more unscheduled assessments with non-missing results and the same distance to the planned study day, the assessment prior to the planned study day will be used in deriving visit window. For example, if the lab assessment was done on both study day -1 and 1, then the assessment on -1 study day will be used for visit windowing.
- For ECG assessment associated with study drug dose, only assessments where time point (prior to infusion or 2 hr after infusion) are not missing will be considered for the analysis.

Table 1 Visit Window Definition for Safety Assessment

| Assigned Study Day (Inclusive) | | Planned Study Day (AWTARGET) | Analysis Visit (N) (AVISITN) | Analysis Visit (AVISIT) | Assessment |
|--------------------------------|-----------|------------------------------|------------------------------|-------------------------|----------------------|
| From (AWLO) | To (AWHI) | | | | |
| ~ | 1 | | 1 | Baseline | Lab, Vital Sign, ECG |

| | | | | | |
|-----|-----|-----|----|---------------------|----------------------|
| 1 | 1 | 1 | 2 | Week 1 Day 1* | ECG |
| 5 | 11 | 8 | 3 | Week 2 Day 5-11 | Core Serum Chemistry |
| 12 | 18 | 15 | 4 | Week 3 Day 12-18 | Lab, Vital Sign, ECG |
| 19 | 25 | 22 | 5 | Week 4 Day 19-25 | Core Serum Chemistry |
| 26 | 32 | 29 | 6 | Week 5 Day 26-32 | Lab, Vital Sign, ECG |
| 33 | 39 | 36 | 7 | Week 6 Day 33-39 | Core Serum Chemistry |
| 40 | 50 | 43 | 8 | Week 7 Day 40-50 | Lab, Vital Sign, ECG |
| 51 | 64 | 57 | 10 | Week 9 Day 51-64 | Lab, Vital Sign, ECG |
| 65 | 78 | 71 | 12 | Week 11 Day 65-78 | Lab, Vital Sign, ECG |
| 79 | 92 | 85 | 14 | Week 13 Day 79-92 | Lab, Vital Sign, ECG |
| 93 | 106 | 99 | 16 | Week 15 Day 93-106 | Lab, Vital Sign |
| 107 | 120 | 113 | 18 | Week 17 Day 107-120 | Lab, Vital Sign |
| 121 | 134 | 127 | 20 | Week 19 Day 121-134 | Lab, Vital Sign |
| 107 | 148 | 127 | 20 | Week 19 Day 107-148 | ECG |
| 135 | 148 | 141 | 22 | Week 21 Day 135-148 | Lab, Vital Sign |
| 149 | 162 | 155 | 24 | Week 23 Day 149-162 | Lab, Vital Sign |
| 163 | 176 | 169 | 26 | Week 25 Day 163-176 | Lab, Vital Sign |
| 149 | 190 | 169 | 26 | Week 25 Day 149-190 | ECG |
| 177 | 190 | 183 | 28 | Week 27 Day 177-190 | Lab, Vital Sign |
| 191 | 204 | 197 | 30 | Week 29 Day 191-204 | Lab, Vital Sign |
| 205 | 218 | 211 | 32 | Week 31 Day 205-218 | Lab, Vital Sign |
| 191 | 232 | 211 | 32 | Week 31 Day 191-232 | ECG |

* Only applies to 2 hr post dose.

Calculation of duration:

Duration will be calculated by the difference of start and stop date + 1 (e.g. survival time (days) = date of death – date of first study treatment + 1), unless otherwise specified.

Conversion of days to months or years:

The following conversion factors will be used to convert days into months or years: 1 month = 30.4375 days, 1 year = 365.25 days.

Significance level:

The overall significance level is 2.5% one-sided. The confirmatory statistical test for the primary efficacy endpoint analysis is described in Section 16.1 along with procedures for controlling the overall type I error rate. All other statistical analyses performed on the secondary and other endpoints defined in this SAP are exploratory.

Confidence intervals will be two-sided with a confidence probability of 95%, if not otherwise specified.

Presentation of continuous and qualitative variables:

Continuous variables will be summarized using descriptive statistics i.e., number of non missing values and number of missing values, [i.e. n (missing)], mean, median, standard deviation (StdDev), minimum, maximum and first and third quartile (Q1 and Q3).

Qualitative variables will be summarized by counts and percentages. Unless otherwise stated the calculation of proportions will include the missing category. Therefore counts of missing observations will be included in the denominator and presented as a separate category.

All data recorded during the trial will be presented in individual data listings performed on the Safety analysis set.

Handling of missing data:

Unless otherwise specified in this SAP, all data will be evaluated as observed, and no imputation method for missing values will be used, unless otherwise specified.

In all subject data listings imputed values will be presented. In all listings imputed information will be flagged.

Missing statistics, e.g. when they cannot be calculated, should be presented as “nd”. For example, if n=1, the measure of variability (StdDev) cannot be computed and should be presented as “nd”.

Handling of incomplete dates:

Incomplete dates for disease history (initial diagnosis date, date of documented, locally advanced or metastatic disease diagnosis) will be imputed as follows:

- If the day is missing, it will be imputed to the 15th day of the month.
- If both day and month are missing and the year is prior to the year of the first study treatment, the month and day will be imputed as July 1st.
- If both day and month are missing and the year is same as the year of the first study treatment, the month and day will be imputed as January 1st.
- If the date is completely missing, no imputation will be performed.

Incomplete AE-related dates will be handled as follows:

- In case the onset date is completely missing or the onset is in the same month and year (if the day is missing) as the start of trial treatment then the onset date will be replaced by the minimum of start of trial treatment and AE resolution date.
- In all other cases the missing onset day or missing onset month will be replaced by 1.
- Incomplete stop dates will be replaced by the last day of the month (if day is missing only), if not resulting in a date later than the date of subject's death. In the latter case the date of death will be used to impute the incomplete stop date.
- In all other cases the incomplete stop date will not be imputed. If stop date of AE is after date of cut-off outcome of AE is ongoing at cut-off.
- Further information after cut-off (like fatal outcome) might be taken from Safety database and included separately into CTR.

Incomplete prior/concomitant medication dates will be imputed as follows:

- If the medication date is missing completely, then the medication date will be replaced by the start of trial treatment.
- If the day of medication date is missing, but the month and year are equal to the start of trial treatment, then the medication date will be replaced by the start of trial treatment. For example, if the medication start date is --/JAN/2015, and trial treatment start date is 15/JAN/2015, then the imputed medication start date will be 15/JAN2015.
- If both the day and month of medication start date are missing but the start year is equal to the start of trial treatment, then the medication date will be replaced by the start of trial treatment. For example, if the medication start date is --/--/2014, and trial treatment start date is 19/NOV/2015, then the imputed medication start date will be 19/NOV/2014.
- In all other cases the missing medication day or missing medication month will be replaced by 1.
- Incomplete stop date will be replaced by the last day of the month (if day is missing only), if not resulting in a date later than the date of subject's death. In the latter case the date of death will be used to impute the incomplete stop date.
- In all other cases the incomplete medication stop date will not be imputed.

For reporting conventions, mean and median should generally be displayed to one more decimal place than the raw data and standard deviation should be displayed to two more decimal places than the raw data. Percentages will be reported to one decimal place. The rounding will be performed to closest integer / first decimal using the common mid-point between the two consecutive values. E.g. 5.1 to 5.4 will be rounded to an integer of 5, and 5.5 to 5.9 will be rounded to an integer of 6.

All statistical analyses will be performed using SAS® Version 9.2 or higher, or R (www.r-project.org), version 2.15.2 or higher.

12 Trial Subjects

The subsections in this section include specifications for reporting subject disposition and treatment/trial discontinuations. Additionally procedures for reporting protocol deviations are provided.

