5.3 Selection of Trial Population

5.3.1 Inclusion Criteria

For inclusion in the trial, all of the following inclusion criteria must be fulfilled:

1. Signed written informed consent
2. Male or female subjects aged ≥ 18 years
3. Histologically proven MCC
 - a. Confirmation of the diagnosis by immunohistochemistry detection of CK20 (or other appropriate cytokeratin expression such as pancytokeratin, AE1/AE3, or Cam5.2; local laboratory testing) in the tumor cell is mandatory
 - b. Subjects must have metastatic disease; subjects with non-metastatic MCC that is only recurrent or unresectable are NOT eligible; for Part B, M1 status must be confirmed at entry
 - c. For Part A: Subjects must have received at least 1 line of chemotherapy for the treatment of metastatic MCC and must have progressed after the most recent line of chemotherapy that was administered. Subjects must have received at least one of the following chemotherapy regimens for treatment of metastatic MCC: Cyclophosphamide, topotecan, doxorubicine, epirubicin, vincristine, carboplatin, cisplatin, etoposide in combination with carboplatin or cisplatin

- d. For Part B: Subjects must not have received any prior systemic treatment for metastatic MCC. Prior chemotherapy treatment in the adjuvant setting (no clinically detectable disease; no metastatic disease) is allowable if the end of treatment occurred at least 6 months prior to study start
4. For Part A: Collection of biopsy material is required (fresh biopsy or recent biopsy [within 4 weeks prior to enrollment], for subjects unable to provide a fresh or recent biopsy, archival material is acceptable).

For Part B:

- 1) Priority: A recently obtained formalin-fixed, paraffin-embedded (FFPE) block containing tumor tissue (preferably within 6 months). If no tumor tissue is available, fresh biopsy will be required
 - 2) Priority: If the tumor containing FFPE tissue block cannot be provided in total, sections from this block should be provided that are freshly cut (within 1 week). Preferably, 25 slides should be provided; if not possible, a minimum of 10 slides in consultation with the Medical Monitor is required
5. ECOG PS of 0 to 1 at trial entry
 6. Estimated life expectancy of more than 12 weeks
 7. Disease must be measurable with at least 1 unidimensional measurable lesion by RECIST 1.1 (including skin lesions)

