7.3 Assessment of Efficacy

All radiographic images and physical findings including photographs (skin lesion mapping) and physical assessments used for the determination of disease progression must be submitted to the IERC vendor and will be reviewed by an IERC (see Section 5.1.2.2). The IERC will make the determination as to whether the criteria for tumor response or progression according to RECIST 1.1 have been met.

For each subject, tumor response assessment will be performed by CT scan or MRI (if MRI is used, CT of chest is mandatory; for trial sites in Germany, only MRI is to be used) imaging of the chest/abdomen/pelvis at a minimum plus other anatomical sites as specifically required) and other established assessments of tumor burden if CT / MRI imaging is insufficient for the individual subject. All the scans performed at baseline and other imaging performed as clinically required (other supportive imaging) need to be repeated at subsequent visits. In general, lesions detected at baseline need to be followed using the same imaging methodology and preferably the same imaging equipment at subsequent tumor evaluation visits. If lesions are no longer detectable, the same anatomical sites evaluated at baseline must be followed at every tumor assessment visit using the same imaging and photography methods as used at baseline.

An examination for clinical lesions, including mapping of skin lesions, should also be conducted at each tumor assessment. For skin lesions to be identified as target lesions, a minimum longest diameter of 10 mm is required. In the case of skin lesions, documentation by color photography using standardized procedures, including an accurate measurement scale within the image, is required. Refer to [Appendix IV](#) for standardized photography procedures with detailed requirements for lesion selection and photographic image acquisition. Clinical lesions will be considered measurable only when they are superficial and visible (for example, skin nodules, palpable lymph nodes). Skin lesions can be used as target lesions using measurements by caliper if they fulfill RECIST 1.1 for target lesions. The presence of new cutaneous lesions will be considered diagnostic of progression for RECIST 1.1, and any lesions detected by physical examination only should be documented by photography.

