A brain CT / MRI scan is required at Screening if not performed within the previous 6 weeks. Brain CT / MRI scans should be performed, if clinically indicated by development of new specific symptoms (for trial sites in Germany, only MRI is to be used).

A bone scan should be done at Screening and beyond as clinically indicated.

For each subject, the Investigator will designate 1 or more of the following measures of tumor status to follow for determining response: CT or MRI images of primary and/or metastatic tumor masses, physical examination findings, and the results of other assessments. All available images collected during the trial period will be considered. The most appropriate measures to evaluate the tumor status of a subject should be used. The measure(s) to be chosen for sequential evaluation during the trial have to correspond to the measures used to document the progressive tumor status that qualifies the subject for enrollment. The tumor response assessment will be assessed and listed according to the schedule of assessments (refer to [Appendix I](#)).

Tumor responses to treatment will be assigned by the IERC based on the evaluation of the response of target, nontarget, and new lesions according to RECIST 1.1 (all measurements should be recorded in metric notation, see [Eisenhauer 2009](#)).

- To assess objective response, the tumor burden at baseline will be estimated and used for comparison with subsequent measurements. At baseline, tumor lesions will be categorized in target and nontarget lesions as described in [Eisenhauer 2009](#).

Results for these evaluations will be recorded with as much specificity as possible so that pre- and post-treatment results will provide the best opportunity for evaluating tumor response.

Any CR or PR should be confirmed, preferably at the scheduled 6-week interval, but no sooner than 5 weeks after the initial documentation of CR or PR. Confirmation of PR can be confirmed at an assessment later than the next assessment after the initial documentation of PR.

The Investigator may perform scans in addition to a scheduled trial scan for medical reasons or if the Investigator suspects PD.

CCI

CCI

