16.3 Analysis on Subgroups

Analysis on subgroups as defined in Section 10 will be performed for the primary and key secondary efficacy endpoints. In addition, the odds ratio and its 95% CI corresponding to the ORR of each subgroup relative to the reference subgroup will be calculated, and the p-value from Fisher's exact test will be provided to assess the association between each subgroup factor and ORR. Furthermore, to compare PFS time and OS time within each subgroup factor, the hazard ratio and its 95 % CI of each subgroup relative to the reference subgroup will be calculated using Cox proportional hazards model.

A forest plot will be created to graphically present ORR and its 95% CIs for the ITT analysis set and all the subgroups.

CCI [REDACTED]. In case of low number of subjects within a category (< 5 subjects, which is about 5% of the study population), subgroups will be pooled.

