- Subject has a tumor assessment > 5 weeks after first dose of study treatment (unless PD or death is observed before that time, in which case the subject will not be excluded from the PP analysis set).

The PP analysis set will be used for additional sensitivity analyses for the primary and secondary efficacy endpoints. If the PP analysis set includes at least 95% of subjects in the safety analysis set, additional efficacy analyses on the PP analysis set will be omitted as the differences in the results based upon these two analysis sets are expected to be negligible.

Subgroup Analysis Sets

The below subgroup analyses will be performed on primary and key secondary efficacy endpoints. Since the study is not powered for any subgroup analysis, CCI.

The following subgroups will be defined:

- Age Group 1:
 - Age < 65 years (Reference)
 - Age \geq 65 years
- Age Group 2:
 - Age \leq Median (Reference)
 - Age > Median
- Gender
 - Male (Reference)
 - Female
- Race
 - Caucasian / White (Reference)
 - Asian
 - Black/ African American
 - Other
- Pooled Geographical Region:
 - North America
 - Europe (Reference)
 - Asia
 - Rest of the World (Australia and/or Latin America will be included as additional pooled geographical regions if including \geq 10 subjects in the FAS)

CCI

CCI

- Time from initial diagnosis to study entry
 - ≤ 3 months (Reference)
 - > 3 months and ≤ 1 year
 - > 1 year
- Time from first occurrence of metastatic disease to study entry
 - ≤ 3 months (Reference)
 - > 3 months and ≤ 1 year
 - > 1 year
- ECOG PS at baseline
 - ECOG PS 0 (Reference)
 - ECOG PS 1
- Disease Burden by IERC assessment
 - Baseline SLD \leq Median (Reference)
 - Baseline SLD $>$ Median
- Presence of visceral metastases at baseline. Target or non-target lesions that are categorized as neither skin (including soft tissue and eye) nor lymph node lesions per IERC assessment are classified as visceral metastases.
 - Present
 - Absent (Reference)
- Number of prior systemic chemotherapies
 - 0 Prior Therapy (Reference)
 - ≥ 1 Prior Therapies

- Site of primary tumor (representing known versus unknown primary status)
 - Skin
 - Non-Skin (Reference)
- Lymph node disease only at Baseline per IERC assessment
 - Yes (Reference)
 - No
- Baseline CD8 T-cell density (expressed in % CD8+ cells and number of CD8+ cells/mm²)
 - < Median (Reference)
 - ≥ Median

11 General Specifications for Statistical Analyses

Data handling after cut-off date:

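### The Part A SAP defines visceral metastases by the investigator category *metastatic* with no anatomical site, so read literally a nodal or skin metastasis with that label counts as visceral

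*SAP*

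**What the plan says.** Part A SAP, Section 10 (Additional Subgroup Analysis Sets), has a factor for visceral metastases at baseline with levels Present and Absent, Absent being the reference. Its whole definition is: "Target or non-target lesions that are categorized as “metastatic” per investigator assessment are classified as visceral metastases". Nothing else in the Part A SAP narrows it.

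Part B SAP, Section 10, has a factor of the same name with the same two levels. There the lesions that count are those "categorized as neither skin (including soft tissue and eye) nor lymph node lesions per IERC assessment are classified as visceral metastases".

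Part A SAP, Section 16.3, puts the factor to use: "Analysis on subgroups as defined in Section 10 will be performed for the primary and key secondary efficacy endpoints". The outputs are an odds ratio and Fisher test for ORR, hazard ratios for PFS and OS, and an ORR forest plot. (Section 10 of the same SAP says only that these analyses may be done.) Section 16.3 also has a pooling rule: "In case of low number of subjects within a category (< 5 subjects", categories are combined.

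Part A SAP, Section 11 (Significance level), sets the status of everything beyond the primary test: "All other statistical analyses performed on the secondary and other endpoints defined in this SAP are exploratory".

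**The concern.** *Metastatic* describes spread and *visceral* describes site. The Part A rule takes the first and reports it as the second. Protocol Section 7.3 allows cutaneous disease to be measured ("Skin lesions can be used as target lesions using measurements by caliper"), and where it lists what the investigator may follow it speaks of "CT or MRI images of primary and/or metastatic tumor masses". That contrast is primary against metastatic, not visceral against nodal or skin. If the investigator's lesion category works the same way, subjects with only nodal or skin metastases fall into Present.

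The Part A results for this factor would then not describe visceral disease. A reader setting the Part A and Part B forest plots side by side would also see one label for two different constructs.

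**Working it through.** The plan gives no figure for this factor, so there is none to reproduce. The check is a comparison of texts, followed by an illustration.

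**1. The two rules applied to the same lesions**

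| Baseline lesion, investigator category *metastatic* | Part A rule, read literally | Part B rule |
|---|---|---|
| Liver or lung | Present | Present |
| Lymph node | Present | not counted |
| Skin or soft tissue | Present | not counted |

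The rules differ in criterion (label against site) and in assessor (investigator against IERC).

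**2. What the literal reading implies.** Protocol Section 5.3.1 requires: "Subjects must have metastatic disease; subjects with non-metastatic MCC that is only recurrent or unresectable are NOT eligible". If *metastatic* covered every metastatic deposit, few subjects could be Absent, yet the SAP keeps Absent as the reference level. That is evidence for a narrower code.

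**3. Illustration of direction.** From the documents: 88 subjects treated (Part A SAP Section 7), and a 35% ORR, which is itself a design assumption. Everything else here is assumed: 44 truly visceral subjects with 11 responders (25%) and 44 non-visceral with 20 (45%). Overall this is 31/88 = 35.2%.

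True odds ratio = (11/33)/(20/24) = 0.40, Fisher two-sided p = 0.073.

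Now suppose 22 non-visceral subjects, r of them responders, are coded Present. The observed odds ratio is [(11 + r)/(55 − r)] / [(20 − r)/(2 + r)].

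| r (ORR in the 22) | Present | Absent | Odds ratio | Fisher p |
|---|---|---|---|---|
| 7 (32%) | 18/66 | 13/22 | 0.26 | 0.010 |
| 10 (45%) | 21/66 | 10/22 | 0.56 | 0.305 |
| 13 (59%) | 24/66 | 7/22 | 1.22 | 0.800 |

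The observed value crosses the true 0.40 between r = 8 (0.34) and r = 9 (0.43). If the relabelled subjects respond like those left in Absent (r = 10), the contrast shrinks towards no difference. Otherwise it can be exaggerated or reversed. The outer rows need a 27-point ORR difference inside the non-visceral group (13/22 against 7/22), and nothing in the documents supports one.

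**4. Illustration of the size of Absent.** With X ~ Binomial(88, p) and p the assumed share of subjects coded Absent, P(X ≤ 4) is 0.97 at p = 2%, 0.55 at 5% and 0.05 at 10%. Below 5 subjects the pooling rule merges the two levels and the comparison disappears.

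**The case against.** The strongest reply is that this is loose wording and not a wrong analysis. Four parts of it deserve weight.

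- **The label looks like a code.** The SAP puts *metastatic* in quotation marks and says lesions are categorised as such. That reads like an eCRF value, and the code list may hold separate entries for skin and lymph node. With the retained Absent level, this favours a narrower meaning.
- **The Part B log claims alignment.** Its modification history for version 2.0 says the Section 10 subgroups were changed to agree with Part A. The version 3.0 entries itemise other subgroup changes and none to this factor. This suggests the sponsor thought the two rules equivalent. It shows intent and not proof: the two subgroup lists are not identical, and both versions also record minor editorial changes.
- **Protocol 7.3 is weak evidence.** It lists physical examination findings separately from imaged masses, so it does not show that investigators labelled skin or nodal lesions *metastatic*.
- **Protocol 5.5.1 came later.** It now speaks of metastatic lesions as either nodal or visceral, but Appendix V shows that paragraph entered with Amendment 11 in May 2018. Part A SAP version 3.0 is dated March 2016. The paragraph cannot settle the Part A eCRF vocabulary.

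All four stand, and together they mean misclassification is unproven. They do not rescue the sentence. The SAP neither cites nor describes a code list, so the flag cannot be checked or reproduced from it.

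**Conclusion.** The point holds as a defect in a stated rule: the Part A definition names no site and, read literally, differs from the Part B definition of the same factor. It is minor. Confidence in the reading of the text is high; confidence that any result changed is low, and the effect may be nil.

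A reader might infer that Part A subjects with only nodal or skin disease were in fact counted as visceral, or that the reported subgroup contrast is biased by some stated amount. The documents support neither. The code list is absent, the indirect evidence points to a narrower code, and the split, response rates and relabelled share in the illustration are invented. The illustration shows only that bias, if present, has no fixed direction.

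The reach is one factor in the exploratory Part A subgroup analyses. The primary ORR test, its thresholds and its type I error control do not depend on it. The documents plan no formal comparison of this subgroup across parts, so comparability concerns readers and not a planned test.

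**What to change.** First, check what the eCRF value *metastatic* covers.

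- **If it already excludes skin and nodal lesions:** the flag stands. Correct the sentence in Part A SAP Section 10 to say so.
- **If it does not:** define the factor as Present when any baseline target or non-target lesion is at a recorded site that is neither skin (including soft tissue and eye) nor lymph node. This is the sponsor's own Part B criterion. Keep the investigator as assessor unless IERC site data are available; Protocol Section 2.3.2 describes a different IERC process for Part A, so that needs confirming. Re-derive the flag, rerun the outputs for this factor, and label them post hoc where Part A results are already reported (Protocol Section 10.6.2 cites Part A publications).

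The cost is one SAP sentence, a look at the code list, confirmation that lesion site was recorded and, in the second case, one re-derived flag and its tables. No new data collection is proposed.
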